For events identified any time after the index date such as intra-uterine infection, we will calculate crude incidence and 95% CI for each adverse event for the exposed and unexposed groups. The incidence of each maternal adverse event during pregnancy will be calculated separately and will consist of the total number of women with the condition in the numerator and the total person time in the denominator. The person-year for a pregnant woman will be the time from the index date to the date of each adverse event, end of the pregnancy, or disenrollment, whichever comes first. The adjusted relative risk with CI will be estimated by a Poisson regression model accounting for the follow-up time with adjustment for potential confounders. If the outcome is common (i.e., incidence > 2%), a Poisson regression model with robust variance estimation will be used to estimate the relative risk. For primary endpoints, a two-sided 98.75% CI will be used for the relative risk with multiple comparison adjustment, while for secondary endpoints a two-sided 95% CI will be used.

Congenital anomalies will be identified at birth and through 6 months of age among infants born in KPSC hospitals. Most congenital anomalies are diagnosed by 6 months of age (35). The prevalence of congenital anomalies (overall, by type, at birth, and through 6 months of age) will be calculated as the number of infants with a congenital anomaly in the numerator and the total number of infants born in KPSC hospitals in the denominator. The proportion of live births without congenital anomalies will be calculated as 1 minus the proportion of live births with congenital anomalies among all KPSC live born infants. The adjusted relative risk with 95% CI will be estimated by a Poisson regression model with adjustment for potential confounders. If the outcome is common (i.e., incidence > 2%), a Poisson regression model with robust variance estimation will be used to estimate the relative risk.

The following table outlines the planned method of analysis by endpoint.

Table 7 Analytic population and statistical methods by endpoint (amended 12 November 2019)

Primary endpoints	Analytic population	Statistical Methods
Preeclampsia and eclampsia	All pregnant women eligible for inclusion/exclusion criteria	Adjusted Poisson regression model accounting for follow up time, with robust variance estimate

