### **3.2 Study population, exposures, outcomes and covariates**

#### **3.2.1 Study populations/subgroups**

##### *Study population for main analysis (primary objective and secondary objective #1)*

- Pregnant women received prenatal care at KPSC
- Exposed cohort: vaccinated with Boostrix on the 1st day of the 27th week of pregnancy or later during the pregnancy and were not vaccinated with any other Tdap vaccine at any other time during the pregnancy or
- Unexposed cohort: pregnant at least one day during the approximate estimated period between 1/1/2012-12/31/2013 and did not receive any Tdap vaccine during the pregnancy
- Continuous membership (allowing up to a 31-day gap) between the 1st day of the 27th week of pregnancy and the index (vaccination) date

The unexposed cohort will be 1:1 matched to the exposed cohort on age at pregnancy start ( $\pm 1$  year), race/ethnicity (White, Black, Hispanic, Asian, and Other), and multiple gestation (yes/no). Every unexposed woman will be assigned an index date that is determined by the number of days from pregnancy start to the Boostrix vaccination date of her matched exposed woman. The same number of days calculated in the exposed woman will be added to the pregnancy start of the unexposed woman to determine her index date.

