##### *Subgroups for endpoint-specific analysis*

For some maternal and infant AEs (endpoints), additional restriction criteria will be applied. We will exclude individuals who do not meet the restriction criteria, but not the matched pair. Analysis will be conducted on a subgroup of the population:

- Small for gestational age (SGA): Infants 1) live born, 2) singleton, and 3) born in KPSC hospitals. Rationale: The evaluation of SGA is limited to singleton births because the reference values for SGA definition are established based on singleton births. The birth weight of infants born outside KPSC hospitals is not captured in claims, and such infants are therefore excluded for this endpoint.

- Preterm delivery: Pregnant women 1) with live birth and 2) with index (vaccination) date prior to 37 weeks gestation. Rationale: Pregnant women with an index (vaccination) date on or after 37th week of gestation are not at risk of preterm delivery, and are therefore excluded for this endpoint.
- Preterm pre-labor rupture of membranes (PPROM): Pregnant women with index (vaccination) date prior to 37 weeks gestation. Rationale: Pregnant women with an index (vaccination) date on or after 37th week of gestation are not at risk of PPROM, and are therefore excluded for this endpoint.
- Transfusion during delivery hospitalization: Pregnant women with delivery hospitalization. Rationale: Transfusion can be captured by procedure codes during the delivery hospitalization.
- Stillbirth/fetal death: Pregnant women with pregnancy outcome. Rationale: Pregnant women with unknown pregnancy outcome are considered as missing data, and are therefore excluded for this endpoint.
- Neonatal death (within 28 days of birth) and congenital anomalies at birth and through 6 months of age: Infants 1) live born and 2) born in KPSC hospitals. Rationale: Infants born outside KPSC hospitals may not be captured and may not be able to be linked back to their pregnant mothers, and are therefore excluded for this endpoint.

Analysis for preeclampsia and/or eclampsia, intra-uterine infections, poor fetal growth, placental abruption, and maternal death will be conducted on all pregnant women eligible for the main analysis and descriptive analysis.

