For poor fetal growth, placental abruption, PPROM, and maternal death, the incidence will consist of the total number of women with the condition in the numerator and the total person time in the denominator. For poor fetal growth, placental abruption, and PPROM, the person-time for a pregnant woman will be the time from the index date to the date of each adverse event, end of the pregnancy, or disenrollment, whichever comes first. For maternal death, the person-time for a pregnant woman will be the time from the index date to the date of death, 42 days after delivery, or disenrollment, whichever comes first. The unadjusted and adjusted relative risk with 95% CI will be estimated by Poisson regression models, or Poisson regression models with robust error variances if incidence >2%, accounting for the follow-up time without and with adjustment for potential confounders.

For stillbirth/fetal death and transfusion during delivery hospitalization, the incidence will consist of the total number of women with the condition in the numerator and the number of women for whom the condition can be assessed in the denominator. The unadjusted and adjusted relative risk with 95% CI will be estimated by Poisson regression models, without and with adjustment for potential confounders.

Neonatal death and congenital anomalies will be identified among infants born in KPSC hospitals. The incidence of neonatal death will be calculated as the number of neonatal deaths in the numerator and the total number of infants born in KPSC hospitals in the denominator. The prevalence of congenital anomalies (overall, by type) will be calculated as the number of infants with a congenital anomaly in the numerator and the total number of infants born in KPSC hospitals in the denominator. The proportion of live births without congenital anomalies will be calculated as 1 minus the proportion of live births with congenital anomalies among all KPSC live born infants. The unadjusted and adjusted relative risk with 95% CI will be estimated by Poisson regression models, or Poisson regression models with robust error variances if incidence >2%, without and with adjustment for potential confounders.

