#### **4.4 Analysis of pregnant women vaccinated before the 27th week of gestation**

The analysis of pregnant women vaccinated with Boostrix before the 27th week of gestation will be descriptive. Due to the expected extremely small sample size, no formal hypothesis testing is planned.

The size of the study population and subgroups will be described. See Appendix A, Table Shell 6 for details. Baseline characteristics of pregnant women and their KPSC live born infants will be described. Continuous variables will be summarized by mean, median, Q1, Q3, range, and standard deviation; categorical variables will be summarized by frequency and percentage. See Appendix A, Table Shell 7 and Table Shell 8 for details.

The number of events for each primary and secondary endpoint in Table 1 among pregnant women vaccinated with Boostrix before the 27th week of gestation will be reported. The incidence will be calculated as the total number of women with the condition in the numerator and the number of women (or total person time) for whom the condition can be assessed in the denominator. Since we will likely observe no events or few events for most of the endpoints, the 95% Wilson score interval with continuity correction will be provided ([7](#)). See Appendix A, Table Shell 9 for details.

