Apgar 1 score, n (%)	
≤3	
4-6	
≥7	
Missing	
Apgar 5 score, n (%)	
≤3	
4-6	
≥7	
Missing	

Table 9. Incidence of primary and secondary endpoints among pregnant women vaccinated with Boostrix before the 27th week of gestation

	Exposed			Incidence per 1000 persons or person-years (95% CI)
	Number of Persons	Number of Person years	Number of events	
Primary endpoints				
Pre-eclampsia and eclampsia a				N/A*
Intra-uterine infections a				
Small for gestational age b				N/A*
Preterm delivery c				N/A
Secondary endpoints				
Poor fetal growth, IUGR a				
Placental abruption a				
Preterm pre-labor rupture of membranes (PPROM) d				
Maternal death a				
Stillbirth/fetal death e				N/A
With congenital anomalies				N/A
Spontaneous abortion e				N/A
With congenital anomalies				N/A
Therapeutic abortion e				N/A
With congenital anomalies				N/A
Transfusion during delivery hospitalization f				N/A
Neonatal death g				N/A
Congenital anomalies at birth and through 6 months of age f				N/A
Congenital anomalies of nervous system				N/A
Congenital anomalies of eye				N/A
Congenital anomalies of ear, face, or neck				N/A
Congenital anomalies of cardiovascular system				N/A
Congenital anomalies of respiratory system				N/A
Clefts				N/A
Congenital anomalies of upper gastrointestinal system				N/A
Congenital anomalies of lower gastrointestinal system				N/A
Congenital anomalies of genital organs				N/A
Congenital anomalies of renal system				N/A
Congenital anomalies of musculoskeletal system				N/A
Congenital anomalies of limb				N/A
Congenital anomalies of integument				N/A
Other and unspecified congenital anomalies				N/A
Number of congenital anomalies (based on body system) per infant				N/A
0				N/A
1				N/A
2				N/A
3				N/A
≥4				N/A

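### PPROM person-time runs past 37 weeks, when the SAP says women are no longer at risk, so PPROM rates are too low in both cohorts; SAP 4.4 names only a binomial interval for results that may be person-time rates

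*SAP*

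**What the plan says.** **PPROM person-time.** SAP 4.3 groups three endpoints under one rule: "For poor fetal growth, placental abruption, and PPROM, the person-time for a pregnant woman will be the time from the index date to" the event, the end of pregnancy or disenrollment, whichever is earliest. This repeats the general rule in protocol 6.2.2, which counts "the time from the index date to the date of each adverse event, end of the pregnancy, or disenrollment, whichever comes first". Neither document adds a stop for PPROM.

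SAP 3.2.1 (subgroups for endpoint-specific analysis) removes women whose index date is at or after the 37th week, on the ground that they "are not at risk of PPROM, and are therefore excluded for this endpoint".

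The same paragraph of SAP 4.3 gives another endpoint its own stop: "For maternal death, the person-time for a pregnant woman will be the time from the index date to the date of death, 42 days". The 42 days are counted from delivery, and leaving the health plan also ends follow-up.

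On matching, SAP 3.2.1 states: "The same number of days calculated in the exposed woman will be added to the pregnancy start of the unexposed woman". The two members of a pair therefore start follow-up on the same gestational day.

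**Women vaccinated before 27 weeks.** SAP 4.4 sets the denominator as "the number of women (or total person time) for whom the condition can be assessed in the denominator" and says that "the 95% Wilson score interval with continuity correction will be provided". The reference cited for that interval is a paper on the single proportion. Table Shell 9 heads its result column "Incidence per 1000 persons or person-years (95% CI") and its footnotes name no other interval.

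**The concern.** If no PPROM can occur from 37 weeks, time after 37 weeks is not time at risk. SAP 3.2.1 applies that reasoning to women but SAP 4.3 does not apply it to time. A woman indexed at 30 weeks who stays enrolled and delivers at 39 weeks adds two weeks to the denominator during which, on the SAP's own reasoning, she cannot contribute an event. The denominator can only be too large, so the rate per unit of time at risk can only be too low. Table Shell 5 reports this rate for both cohorts. A signal investigation for PPROM under SAP 4.5 would inherit the same denominator in its stratified rates.

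The second point concerns the interval in SAP 4.4. Wilson limits belong to a binomial proportion. If person-time is entered as the binomial sample size, the limits change with the time unit. The SAP does not say how the interval applies to a rate, or which endpoints are per person-time. If the assignment in SAP 4.2 and 4.3 carries over, up to six are: preeclampsia/eclampsia, intra-uterine infection, poor fetal growth, placental abruption, PPROM and maternal death.

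**Working it through.** The documents give no PPROM rate and no PPROM power to reproduce. Their one computed design figure, 95.7% power for a primary endpoint, reproduces (95.71% by the score-test normal approximation) and is not affected by either point.

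**1. Size of the PPROM shortfall**

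Inputs from protocol Table 4 (2016 feasibility data): 15,111 women vaccinated at 27-32 weeks and 3,500 at 33-36 weeks, total 18,611. Weights are 15,111/18,611 = 0.812 and 3,500/18,611 = 0.188.

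Assumed: the centre of each vaccination band, and mean delivery at 38.5 to 39.5 weeks.

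Shortfall = 1 − (37 − mean index) / (mean delivery − mean index).

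| Band centres (weeks) | Mean index | Weeks at risk | Weeks counted (delivery 38.5 to 39.5) | Rate too low by |
|---|---|---|---|---|
| 28 / 34 | 29.13 | 7.87 | 9.37 to 10.37 | 16.0% to 24.1% |
| 29.5 / 34.5 | 30.44 | 6.56 | 8.06 to 9.06 | 18.6% to 27.6% |
| 30 / 35 | 30.94 | 6.06 | 7.56 to 8.56 | 19.8% to 29.2% |

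Example, first row: 1 − 7.87/9.37 = 16.0%.

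The closed form uses means only. Simulation with a spread in delivery age (assumed SD 1.7 weeks, capped at 42 weeks, delivery after index) gives 17.8-24.2% if vaccination falls early in each band and 22.1-29.4% if it is uniform within bands. A separate simulation with uniform index weeks and delivery centred at 38.8 to 39.5 weeks gives 23-29%.

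**2. Effect on the PPROM relative risk**

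Index day is equal within pairs. If delivery timing and disenrollment are also equal, the excess time cancels and the ratio is 1.00. If mean delivery differs by *k* days between cohorts, around 39 weeks:

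Shift = (39 − mean index) / (39 − mean index − k/7).

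- 1 day: 9.872/(9.872 − 0.143) = 1.015 (centres 28/34), up to 1.018 (centres 30/35).
- 3 days: 9.872/(9.872 − 0.429) = 1.045, up to 1.056.

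**3. The interval in SAP 4.4**

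Expected size of the group: 250 × 15,000/19,554, about 192 women (protocol Table 4). Follow-up is assumed at 0.31 to 0.47 years per woman, giving about 60 to 90 person-years.

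Exact Poisson upper limit = χ²(0.975; 2x + 2) / (2 × person-years). Upper 95% limits per 1000 person-years at 60 person-years:

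| Events | Exact Poisson | Wilson, person-years as n | Wilson on 192 women, rescaled |
|---|---|---|---|
| 0 | 61.5 | 75.0 | 78.2 |
| 3 | 146.1 | 148.2 | 155.7 |
| 4 | 170.7 | 170.1 | 179.0 |
| 5 | 194.5 | 191.2 | 201.7 |
| 14 | 391.5 | 363.4 | 389.7 |

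With person-years as n, Wilson is too high up to 3 events and too low from 4. At 90 person-years the crossover is at 6 events (145.0 against 145.1).

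Dependence on the unit, 14 events: 138-363 with person-years as n, and 133-399 with the same time entered in person-months, against 128-392 for exact Poisson.

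**The case against.** The strongest reply is that no decision changes. PPROM is a secondary, signal-detection endpoint. Its signal rule uses the lower 95% limit of the adjusted relative risk, which barely moves. The SAP 4.4 analysis is descriptive. This stands, and it limits the importance of the point.

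A second reply is that SAP 4.3 openly defines events per person-year of pregnancy after index, alike in both cohorts and in line with the protocol, and that the SAP 3.2.1 wording is an eligibility rationale for women indexed late. Extending it to later time in women indexed earlier is indeed an inference, but a direct one: the same woman cannot be at risk of PPROM at 38 weeks merely because her index date was earlier. Shell 5 also shows persons and events, so a reader could form a risk per woman. That does not repair the rate printed beside them.

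Third, the size is assumed. That is correct. Only the direction is certain.

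Fourth, the Wilson result depends on how it is applied. Computed on women and rescaled, it is conservative at small counts and close to Poisson at 14 events (134-390 against 128-392). That is fair, but the SAP does not specify this reading, and at 0 events it is further from Poisson (78.2 against 61.5).

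Finally, the data management plan was not available. The SAP refers to it for the endpoint algorithms but fixes person-time itself, so a different stop there would conflict with SAP 4.3.

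**Conclusion.** Both points hold.

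Followed as written, the plan reports PPROM rates per person-year that are too low per unit of time at risk in both cohorts. The direction is certain. The size, roughly 15-30%, rests on assumed vaccination timing within the Table 4 bands and assumed delivery age. The PPROM relative risk is essentially unchanged if delivery timing and disenrollment are similar in the two eras. A 1-day difference in mean delivery moves it by 1.5-1.8% and a 3-day difference by 4.5-5.6%, which would matter only for a lower confidence limit very close to 1.

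SAP 4.4 leaves the interval for person-time rates undefined. The resulting error depends on the event count, the time unit and the reading adopted, and it is confined to the women vaccinated before 27 weeks. The primary endpoints and the power calculation are untouched. The change should be made because it corrects reported results at little cost.

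**What to change.** 1. In SAP 4.3, end PPROM person-time at the earliest of the event, 37 completed weeks, the end of pregnancy or disenrollment. Protocol 6.2.2 lists only three stops, so record this as a PPROM-specific departure from its general rule, with the rationale, as SAP section 7 requires for analyses that differ from the protocol.
2. In SAP 4.4 and the Table Shell 9 footnotes, list which endpoints are reported per person-time. Keep the continuity-corrected Wilson interval for proportions of women or infants, and use exact Poisson (Garwood) limits for person-time rates.

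The cost is one censoring line, one confidence-interval function, and the SAP wording with its documented rationale. No additional data are needed.

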On October 24, 2012, ACIP voted to recommend Tdap for pregnant women with every pregnancy irrespective of previous Tdap history. In December 2012, the KPSC RIPC followed ACIP guidance and recommended that providers of prenatal care implement a Tdap immunization program for all pregnant women. The guidance indicated that all health-care personnel should administer a dose of Tdap during each pregnancy irrespective of the patient's prior history of receiving Tdap. In order to maximize the maternal antibody response and passive antibody transfer to the infant, optimal timing for Tdap administration was specified between 27 and 36 weeks gestation.

Prior to the conduct of this observational study of Boostrix in pregnancy, Adacel had been the only Tdap vaccine on the KPSC formulary.

Process for identifying pregnancy information

If a woman receives prenatal care at KPSC, her pregnancy is recorded in a pregnancy episode flowsheet. The flowsheet is contained in the woman's medical record and is created at the beginning of the pregnancy. It is appended with all pregnancy encounters including prenatal visits, the hospital admission for birth, as well as any post-partum visits. Pregnancy and birth information at KPSC including maternal age, pre-pregnancy height and weight, perinatal risk factors, prenatal visit information, complications of pregnancy and delivery, and procedures used during labor and delivery are available from the EHR and can be viewed in Health Connect.

Process for linking mothers and infants

As standard of care at KPSC, all infants born in KPSC hospitals are automatically assigned a MRN regardless of whether the mother is a current plan member. If the mother is a current member, the baby's MRN is automatically linked to her medical record in her pregnancy episode flowsheet.

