4.4. Inclusion criteria

- Pregnant women with prenatal care and continuous membership (allowing up to a 31-day gap) at KPSC between the 1st day of the 27th week of gestation and the index (vaccination) date.
- **Exposed cohort** (from the 27th week of gestation): Pregnant women vaccinated with Boostrix on or after the 1st day of the 27th week of gestation; who were not vaccinated with any other Tdap vaccine at any other time during the pregnancy in scope of this study.
- **Unexposed cohort:** Women matched to the exposed cohort and pregnant sometime during the approximate estimated period between 1/1/2012-12/31/2013 and did not receive any Tdap vaccine during the pregnancy in scope of this study.

For the analysis of congenital anomalies among live births, at birth and through six months of age, the following additional inclusion criteria for infants will be applied:

- Live born
- Born in KPSC hospitals

Note: Pregnant women vaccinated with Boostrix during pregnancy before the 27th week of gestation, with membership at the date of vaccination, and who were not vaccinated with any other Tdap vaccine at any other time during the pregnancy in scope of this study will be part of a descriptive analysis (secondary objective).

5. DATA COLLECTION AND MANAGEMENT (amended 12 November 2019)

[figure not shown]
Vaccination and medical event data will be extracted directly from the EHR (Health Connect), which is the legal record of all medical care received within the KPSC system. [Figure 1](#) provides an overview of the data flow for this study. All details of a patient encounter, including diagnoses, procedures, and physician's notes, are entered into the EHR at the point of care. All vaccinations are entered into the EHR when they are given, with vaccine, dose, manufacturer, and lot number entered at the time of vaccination. Vaccinations received outside of the health plan are recorded with appropriate documentation. Records of vaccinations and medical events can only be entered by medical staff. Endpoints of interest will be extracted from the EHR using the pregnancy episode flowsheet, diagnosis codes (ICD-9 and ICD-10 codes), procedure codes, or death records.

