### **3. STUDY DESIGN**

#### **3.1 Overview of study design**

This is an observational retrospective matched cohort study. The study will be conducted among pregnant women who are members of KPSC.

The exposed cohort (from the 27th week of gestation) will consist of pregnant women who received the Tdap vaccine (Boostrix) on or after the 1st day of the 27th week of pregnancy during the vaccination period at ob-gyn clinics of seven selected medical centers. Approximately 15,000 women vaccinated with Boostrix will be included in this study over approximately a one-year period from January 2018 to January 2019.

The unexposed cohort will consist of women, pregnant sometime during the approximate estimated period from 1/1/2012 to 12/31/2013 who never received Tdap vaccine during pregnancy. The unexposed cohort of pregnant women will be matched 1:1 to the exposed cohort of pregnant women for comparisons of maternal and infant AEs between the two cohorts.

Subject-level data will be collected for pregnant women and their infants through the EHR. For each individual pregnant woman, analytical follow up will begin on the date they receive the Boostrix vaccine, or the index date for the unvaccinated cohort, and will end on the date of

disenrollment or the end of pregnancy, whichever came first. For the maternal death endpoint, pregnant women will be followed for 42 days after the end of pregnancy. Infants born in KPSC hospitals will be followed for 6 months.

In addition, women vaccinated with Boostrix before the 27th week of gestation, with membership at the date of vaccination, and who were not vaccinated with any other Tdap vaccine at any other time during the pregnancy will be included for a descriptive analysis (single arm).

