Congenital anomalies at birth and through 6 months of age d			N/A			N/A			N/A	N/A
Congenital anomalies of nervous system			N/A			N/A				
Congenital anomalies of eye			N/A			N/A				
Congenital anomalies of ear, face, or neck			N/A			N/A				
Congenital anomalies of cardiovascular system			N/A			N/A				
Congenital anomalies of respiratory system			N/A			N/A				
Clefts			N/A			N/A				
Congenital anomalies of upper gastrointestinal system			N/A			N/A				
Congenital anomalies of lower gastrointestinal system			N/A			N/A				
Congenital anomalies of genital organs			N/A			N/A				
Congenital anomalies of renal system			N/A			N/A				
Congenital anomalies of musculoskeletal system			N/A			N/A				
Congenital anomalies of limb			N/A			N/A				
Congenital anomalies of integument			N/A			N/A				
Other and unspecified congenital anomalies			N/A			N/A				
Number of congenital anomalies (based on body system) per infant			N/A			N/A			N/A	N/A
0			N/A			N/A			N/A	N/A
1			N/A			N/A			N/A	N/A
2			N/A			N/A			N/A	N/A
3			N/A			N/A			N/A	N/A
≥4			N/A			N/A			N/A	N/A

a Identified among all pregnant women eligible for main analysisb Identified among pregnant women with index (vaccination) date prior to 37 weeks gestationc Identified among pregnant women with pregnancy outcomed Identified among pregnant women with delivery hospitalizatione Identified among KPSC live born infantsf Adjusted for covariates XXX (place holder, covariates may differ for each endpoint)g Poisson regression model with robust variance estimate (place holder)

\* N/A=Not Applicable

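### Congenital anomalies through 6 months are counted over all KPSC-born infants with no rule for infants who leave or die early, and the at-birth analysis that would largely avoid the problem is missing from the SAP

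*SAP*

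**What the plan says.** - **Follow-up.** SAP 3.1 states: "Infants born in KPSC hospitals will be followed for 6 months". It gives no earlier end of follow-up for infants.
- **Population.** SAP 3.2.1 defines the subgroup as "congenital anomalies at birth and through 6 months of age: Infants 1) live born and 2) born in KPSC hospitals". Protocol 4.4 says "the following additional inclusion criteria for infants will be applied" and lists the same two conditions only.
- **Measure.** SAP 4.3 divides "the number of infants with a congenital anomaly in the numerator and the total number of infants born in KPSC hospitals in the denominator". SAP Table 5 plans a Poisson model for anomalies by type, with no follow-up time.
- **Membership.** The mother needs "Continuous membership (allowing up to a 31-day gap) between the 1st day of the 27th week of pregnancy and the index (vaccination) date", so nothing is required after the index date. Protocol 3.1 adds that "all infants born in KPSC hospitals are automatically assigned a MRN regardless of whether the mother is a current plan member".
- **At-birth analysis.** Protocol 6.2.2 plans "The prevalence of congenital anomalies (overall, by type, at birth, and through 6 months of age" as separate quantities. SAP 4.3 keeps only the overall and by-type figures, and Shells 5 and 9 have one combined heading row plus the type rows.
- **Shell footnotes.** In Shell 5 the anomaly row carries footnote d, "Identified among pregnant women with delivery hospitalization"; in Shell 9 it carries footnote f with the same text. SAP Table 5 gives the population as KPSC live-born infants, which is footnote e in Shell 5 and g in Shell 9.
- **Decision rule.** SAP 4.3 declares an elevated risk when the lower 95% limit of the adjusted RR exceeds 1. SAP 5.2 makes no multiplicity adjustment for secondary endpoints.

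**The concern.** A proportion through 6 months is well defined only if each infant in the denominator could have been observed for that long, or if early departures are handled by rule. Here they are not. Elsewhere the plan does handle this. Maternal person-time endpoints are censored at disenrollment. The other delivery-based proportions use women or infants in whom the condition can be assessed. Infants born outside KPSC are excluded because they may not be captured. An infant who leaves before a later diagnosis is equally uncaptured, yet stays in the denominator as a non-case.

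The cohorts are about six years apart, so retention need not be equal. If fewer exposed infants stay, a true increase is masked; if fewer unexposed infants stay, a false signal becomes more likely. SAP 5.1 (missing data), SAP 5.4 (limitations) and the table shells do not mention infant retention, so a reader of the report could not tell which applies.

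**Working it through.** **Stated figures.** The plan gives no power, prevalence or retention figure for congenital anomalies, so there is nothing on this point to reproduce. Its one power figure (95.7%, SAP 3.3) concerns the primary endpoints. It reproduces at 95.71% with a score test and has no bearing here.

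**Formula.** Let d be the share of infants who leave early (d1 exposed, d0 unexposed), L the share of 6-month diagnoses first made after the birth stay, and m the share of those later diagnoses missed in leavers. Diagnoses made before leaving stay in the numerator. If leaving is unrelated to anomaly status,

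observed RR = true RR × (1 − d1·L·m) / (1 − d0·L·m).

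If d1 = d0 the ratio is exactly 1. All values of d, L and m below are assumptions.

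**Scenarios, true RR = 1, d1 = 10%, d0 = 20%.**

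| Scenario | L | m | Observed RR | Retention gap reversed |
|---|---|---|---|---|
| A | 40% | 1 | 0.96/0.92 = 1.04 | 0.92/0.96 = 0.96 |
| B | 40% | 0.5 | 0.98/0.96 = 1.02 | 0.96/0.98 = 0.98 |
| C (type mostly diagnosed late) | 80% | 1 | 0.92/0.84 = 1.10 | 0.84/0.92 = 0.91 |

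**Second parametrization.** Let f be the share of cases diagnosed at birth, and c1 and c0 the shares of later cases captured in the exposed and unexposed cohorts, each between 80% and 95%. Observed RR = [f + (1−f)c1] / [f + (1−f)c0]. For f = 50% this spans 0.92 to 1.08 (for example 0.975/0.90 = 1.083); for f = 70%, 0.95 to 1.05; for f = 90%, 0.98 to 1.02.

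**Effect on the signal rule.** Assume 15,000 infants per cohort, prevalence p, and SE of log RR = √[1/(15,000p) + 1/(15,000p·RR)]. At p = 1% and a spurious RR of 1.05, SE = √(1/150 + 1/157.5) = 0.114 and log(1.05)/SE = 0.43. The chance that the lower limit exceeds 1 is then P(Z > 1.96 − 0.43) = 6.3%, against 2.5% without bias. At p = 0.5% it is 4.9%, and at p = 0.2% about 3.9%. In the other direction, a 5% downward bias on a true RR of 1.2 at p = 1% cuts power from 37.8% to 21.5%.

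**Check of candidate corrections.** Anomalies are present at birth and many are recorded there, so the diagnosis rate is not constant over 6 months.

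- *Keep infants with an event or enrolled to 6 months.* Leavers diagnosed at birth stay in and other leavers drop out. For rare anomalies, A gives (0.96/0.90)/(0.92/0.80) = 0.93, B gives (0.98/0.90)/(0.96/0.80) = 0.91, and C gives (0.92/0.90)/(0.84/0.80) = 0.97. This is worse than no correction in A and B.
- *One person-time offset from birth for all anomalies.* If leavers go soon after birth they contribute almost no time, so A again gives 0.93. An infant diagnosed on the day of birth also has zero follow-up, and log(0) is undefined.
- *Restrict on enrollment to 6 months regardless of case status, retaining deaths.* Cases and infants shrink together: (0.90/0.90)/(0.80/0.80) = 1.00.
- *Person-time only for first diagnoses after the birth stay.* In A, with early leavers, (0.40 × 0.90/0.90)/(0.40 × 0.80/0.80) = 1.00.

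**The case against.** The sponsor could answer as follows.

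- **The measure is a birth prevalence.** Both documents call it prevalence among KPSC-born infants, which is coherent, and several other endpoints are also uncensored proportions. This is true, but those endpoints are fixed at delivery, while this one needs observation to 6 months.
- **Non-member births are few.** In protocol Table 3, 16,147 + 2,728 + 447 = 19,322 of 19,804 vaccinated women (97.6%) had membership to delivery or during the post-vaccine part of pregnancy. This weakens any argument from the record-number rule. It covers 2016 only and says nothing of infants between birth and 6 months.
- **The consequence is limited.** Vaccination is at week 27 or later, and protocol section 7 already urges caution because anomalies most plausibly arise in early pregnancy. The endpoint is hypothesis-generating, and SAP 4.5 requires investigation of any signal. This stands and lowers the severity. However, that caution concerns biology rather than retention, and a bias towards no effect would trigger no investigation.
- **A rule may exist elsewhere.** The identification algorithms are in the data management plan, which is not among the documents. A membership window could be there, although the SAP fixes population and denominator without one.

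A reader might also infer that every infant who leaves is counted as anomaly-free, or that any retention difference distorts the RR. The documents do not support either. Anomalies recorded before departure remain in the numerator, and only unequal loss acting on later diagnoses moves the RR.

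**Conclusion.** The omission is plain in both documents: the 6-month anomaly analysis has no rule for infants who disenroll or die, and an infant lost before a first recorded diagnosis is a non-case for the whole window. Prevalence is understated wherever later diagnoses are missed. The RR is biased only if loss differs between the cohorts. Across the assumed scenarios a true RR of 1 reads about 0.91 to 1.10, the extremes needing a type diagnosed mostly after the birth stay and a 10-point retention gap. Direction and actual size are unknown because no infant retention figure is given; the documents do not show that the result is biased either way.

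Shell 5 marks the overall anomaly RR as not applicable, so the exposure is in the by-type RRs: 14 types, each flagged without multiplicity adjustment. The at-birth analysis in protocol 6.2.2 would be largely immune, and the SAP omits it without a stated reason. The shell footnotes contradict SAP Table 5 and need correcting whatever one thinks of the bias. Severity is minor to moderate.

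**What to change.** 1. In SAP 4.3 and Shells 5 and 9, report anomaly prevalence separately for anomalies recorded at birth among all KPSC-born live infants, as protocol 6.2.2 planned. In SAP 4.3 and Shell 5, also give the at-birth by-type RRs.
2. Keep the through-6-month analysis and add a sensitivity analysis restricted to infants enrolled to 6 months (31-day gap allowed) or who died before then, applied regardless of case status. Deaths must be retained because they may be linked to anomalies. Alternatively, use person-time for first diagnoses after the birth stay only. Do not use a single offset from birth or an event-or-enrolled restriction; both over-correct (0.93 in scenario A).
3. Add to Shell 1 the number and percent of KPSC-born infants with membership through 28 days and through 6 months, by cohort.
4. Change the anomaly footnote in Shells 5 and 9 to KPSC live-born infants.

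The cost is some SAP wording, one enrollment field per infant and a few table rows. The sensitivity analysis will include slightly fewer infants.
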